7.6.2.3 Tertiary Efficacy Variables

For Part 1, no statistical tests will be performed on any of the tertiary efficacy variables. Only descriptive statistics will be shown for each treatment.

For Part 2, the following describes the statistical analyses to be performed.

NRS-R, NRS-A, and AUC of Pain Intensity Scores

For the tertiary efficacy variables NRS-R, NRS-A, and the AUCs of the NRS-R and NRS-A pain intensity scores, the same analyses as those for the primary efficacy variable will be performed, except that the baseline NRS-A score will be used as the covariate for all variables using the NRS-A.

Proportion of Subjects Who are Pain Free

Pain free is defined as an NRS-R pain intensity score of 0 or 1. The number and percentage of subjects who are pain free will be summarized by treatment group for each time point. A chi-square test will be used to compare liposome bupivacaine to placebo.

Total Postsurgical Opioid Consumption Through 24, 36, 48, and 60 Hours

For the tertiary efficacy variables total opioid consumption through each of the time periods, the same analysis as that for the secondary efficacy variable of total opioid consumption through 72 hours will be performed.

Subjects Who Receive Rescue Medication

The category of ‘Subjects who receive no rescue medication’ is defined as subjects who report not taking any medication on the four Rescue Medication eCRFs.

The category of ‘Subjects who only receive the IV hydromorphone bolus’ is defined as subjects who report taking IV hydromorphone (or other opioid medications) on the First Rescue Medication eCRF and report not taking a medication on either of the Second Rescue Medication eCRFs or on the Third Rescue Medication eCRF.

The category of ‘Subjects who receive the IV hydromorphone bolus and a second opioid medication’ is defined as subjects who report taking IV hydromorphone (or other opioid medication) on the First Rescue Medication eCRF and who report taking a medication on either of the Second Rescue Medication eCRFs and report not taking a medication on the Third Rescue Medication eCRF.

The category of ‘Subjects who receive the IV hydromorphone bolus, a second opioid medication, and conventional bupivacaine HCl’ is defined as subjects who report taking IV hydromorphone (or other opioid medication) on the First Rescue Medication eCRF, who report taking a medication on either or both of the Second Rescue Medication eCRFs, and bupivacaine HCl on the Third Rescue Medication eCRF.

The number and percentage of subjects who are in each of the above categories will be summarized by treatment group. A chi-square test will be used to compare liposome bupivacaine to placebo for each of the categories.

Overall Benefit of Analgesia Score Questionnaire

The OBAS is calculated as follows:

1. Add all of the scores of questions one to six.
2. To this number, add four.
3. Subtract the score of question seven from this number.

Summary statistics will be provided by treatment group at each time point. A Wilcoxon Rank Sum test will be used to compare liposome bupivacaine to placebo.

Subject Satisfaction with Postsurgical Pain Control

Subjects will rate their satisfaction with postsurgical pain control as Extremely dissatisfied, Dissatisfied, Neither satisfied nor dissatisfied, Satisfied, or Extremely satisfied at 72 hours and on Day 30. The categories will be summarized by treatment group at each time point. A Wilcoxon Rank Sum test will be used to compare liposome bupivacaine to placebo.

Time to Sensitivity to Cold

Once a subject reports sensitivity to cold on two consecutive evaluations the subject will no longer be tested. The time to sensitivity to cold will be defined as the time of the first of two consecutive evaluations when the subject reports sensitivity to cold. Time to sensitivity to cold will be calculated from the end of surgery. If a subject never reports sensitivity to cold or never reports sensitivity to cold on two consecutive evaluations then the time will be

censored at 72 hours after the end of surgery or at the time of the last follow-up, whichever is earliest. Time of last follow-up will be defined as the later of (1) the last pain assessment, (2) the start time of the last rescue or concomitant medication, or (3) the start time of the last AE.

Time to sensitivity to cold will be analyzed by the Kaplan-Meier method. The n (%) of subjects with sensitivity to cold as well as the n (%) of censored observations will be presented for each treatment group. In addition, Kaplan-Meier estimates in terms of the median and its 95% CI, and the 25th and 75th percentiles will be presented for each treatment group. For Part 2, a log-rank test will be used to compare liposome bupivacaine to placebo.

A plot of the responses to cold sensitivity will be produced for Part 1 and Part 2 separately. The x-axis will show the scheduled hours post-op. The y-axis will be the subject number. An 'X' will be plotted for responses of 'Yes' and an 'O' will be plotted for responses of 'No'.

Figures should be created by site and treatment, combining sites with few subjects, in order to show about 20 subjects per figure.

Incidence of Predefined Treatment-Emergent Opioid-Related AEs

The determination of whether a subject had a treatment-emergent ORAE will be based solely on responses on the Predefined Treatment-Emergent ORAEs eCRF. This was collected in Part 1 only. The number and percentage of subjects who have at least one ORAE will be summarized by treatment group. A chi-square test will be used to compare liposome bupivacaine to placebo.

The number and percentage of subjects who have each of the ORAEs will also be summarized by treatment group, although no statistical tests will be performed.

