11.6. Prior and Concomitant Therapy and Medications

11.6.1. Prior and Concomitant Medications and Therapy

Permitted Prior Medications and Therapy

- Low-dose aspirin for cardioprotection.
- Acetaminophen use is permitted up to the time of surgery.

Restricted Prior Medications and Therapy

- Systemic glucocorticosteroids are not permitted within 1 month of enrollment into this study.
- Initiation of treatment with any of the following medications within 1 month of study drug administration or if the medication(s) are being given to control pain is not permitted: SSRIs, SNRIs, gabapentin, pregabalin (Lyrica), or duloxetine (Cymbalta).
- Long-acting opioid medications, NSAIDs, or aspirin (except for low-dose aspirin used for cardioprotection or acetaminophen) are not permitted within 3 days of study drug administration.
- Dexmedetomidine HCl (Precedex) use is not permitted within 3 days of surgery.
- No opioid medications are permitted within 24 hours of study drug administration.

Concomitant medications

All medications taken within 3 days of study drug administration and up to 72 hours after the end of surgery or until the subject is withdrawn from the study, whichever is sooner, will be recorded on the CRF. Any medications administered in association with AEs occurring during the study will be recorded through Day 30.

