11.6.2. Permitted and Restricted Therapy or Medications During Surgery

Permitted

- Short and ultra-short acting opioids (e.g., fentanyl) will be allowed during surgery.

Restricted

- Bupivacaine cannot be used as the spinal anesthetic.
- No agents are to be admixed with liposome bupivacaine (e.g., epinephrine, dexamethasone, and clonidine).

- Lidocaine and other local anesthetics will not be permitted to be locally administered during the surgery because they are known to interact with liposome bupivacaine resulting in the displacement of bupivacaine and elevated plasma levels.
- Intrathecal opioids.
- The use of opioids other than fentanyl (e.g., morphine, hydromorphone HCl), acetaminophen, ketorolac, or other NSAIDs will not be permitted intraoperatively except for emergency use to treat an AE.
- Entereg (alvimopan) use is prohibited.
- Prophylactic antiemetics or planned postsurgical antiemetics given without regard to the subject's emesis needs is prohibited.

11.6.3. Permitted and Restricted Therapy or Medications After Surgery through 72 Hours After Surgery

Permitted

- Rescue medication use is permitted as described in [Section 11](#).

Restricted

- No other analgesics are permitted within 72 hours after surgery.
- Entereg (alvimopan) use is prohibited.
- Prophylactic antiemetics or planned postsurgical antiemetics given without regard to the subject's emesis needs.
- Dexmedetomidine HCl (Precedex) use is prohibited.

For study purposes, it is important to standardize pain management modalities during the first 72 hours following study drug administration. Therefore, the study staff must adhere closely to the treatment options and requirements noted in the protocol. After 72 hours, the analgesic regimen may be adjusted for each subject individually, as deemed appropriate by the physician responsible for the postsurgical care.

All concomitant medication will be recorded through 72 hours after the end of surgery or until the subject is withdrawn from the study, whichever is sooner.

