6. ANALYSIS SETS

The safety analysis set will include all subjects who receive study drug and will be based on actual treatment received.

The efficacy analysis set will include all subjects in the safety analysis set who undergo the planned surgery and will be based on randomized treatment, regardless of actual treatment received.

The PK analysis set will include all subjects in the safety analysis set who receive liposome bupivacaine, provide sufficient samples to allow for calculation of PK parameters required for analysis, and who do not receive conventional bupivacaine HCl postsurgically.

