7. STATISTICAL METHODS OF ANALYSIS

7.1. General Principles

Descriptive statistics (the number of subjects [n], mean, standard deviation [SD], median, minimum, and maximum) will be used to summarize continuous variables. Means and medians will be presented to one more decimal place than the recorded data. Standard deviations will be presented to two more decimal places than the recorded data. Minimum and maximum values will be presented using the same number of decimal places as the recorded data. Percentages will be presented to one decimal place.

In addition, for PK parameters, geometric means and between-subject coefficient of variations (%CV) will be presented.

Frequency distributions (number [n] and percentage of subjects [%]) will be used to summarize categorical or qualitative variables. In general, the denominator for the percentage calculation will be based upon the total number of subjects in the study population for the treatment groups, unless otherwise specified.

All statistical tests will be performed against a two-sided alternative hypothesis with a significance level of 5% ($\alpha = 0.05$), and all confidence intervals (CIs) calculated will be two-sided 95% CIs. All tests will be declared to be statistically significant if the calculated p-value is ≤ 0.05 unless specified otherwise. Tests for binomial proportions will be conducted (1) using a normal approximation whenever each classification cell for each group to be compared contains expected cell counts of 5 or more subjects, or (2) using an exact method whenever any one classification cell for any one group to be compared contains expected cell counts of fewer than 5 subjects.

All analyses will be performed using SAS[®] Software version 9.2 or later.

Pharmacokinetic parameters will be derived using noncompartmental methods with WinNonlin[®] Professional Version 5.2 or later (Pharsight Corp., Cary, North Carolina).

For the listings, subjects will be listed under their randomized treatment, regardless of actual treatment received. Subjects who are randomized but do not receive study drug will be included in the listings with the treatment group identified as “Liposome bupivacaine xx mg, Not Treated” or “Placebo, Not Treated”, depending on their randomized treatment.

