For the analysis of time to first opioid rescue, time to first opioid rescue will be computed in hours as the date/time of the first opioid rescue minus the date/time of the end of surgery. If a subject is not administered an opioid, the time to first administration will be censored at 72 hours after surgery or at the time of last follow-up, whichever is earliest. Time of last follow-up will be defined as the later of (1) the last pain assessment, (2) the start time of the last rescue or concomitant medication, or (3) the start time of the last AE.

Time to first opioid rescue will be analyzed by the Kaplan-Meier method. The n (%) of subjects administered an opioid as well as the n (%) of censored observations will be presented for each treatment group. In addition, Kaplan-Meier estimates in terms of the median and its 95% CI, and the 25th and 75th percentiles will be presented for each treatment. Log-rank tests will be used to compare each dose of liposome bupivacaine (Part 1) and the one dose of liposome bupivacaine (Part 2) to placebo.

For Part 2, the efficacy measures will be analyzed using a hierarchical fixed-sequence stepwise testing procedure. To protect the Type 1 error rate, the testing will be performed in a sequentially rejective fashion. First, the total postsurgical opioid consumption through 72 hours will be tested. If the test of opioid consumption is significant at the two-sided 0.05 level then, and only then, the time to first opioid rescue will be tested. Each test will be declared positive at the two-sided 0.05 significance level.

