8 Hours	00/00 (00.0)	00/00 (00.0)	0.0000
12 Hours	00/00 (00.0)	00/00 (00.0)	0.0000
24 Hours	00/00 (00.0)	00/00 (00.0)	0.0000
36 Hours	00/00 (00.0)	00/00 (00.0)	0.0000
Etc			

LB = liposome bupivacaine. n/N = Number of subjects with a pain score of 0 or 1 / Number of subjects with a pain score at the time point.

Pain Free is defined as an NRS-R pain intensity score of 0 or 1

[1] P-value is from a chi-square test.

Reference: [Listing 16.5.1.1](#).

Pacira Pharmaceuticals, Inc.
402-C-323

Table 14.2.2.10-2 (Page x of Y)
Total Postoperative Consumption (mg) of Opioid Rescue Pain Medication Through 24, 36, 48, and 60 Hours
Study Part 2
(Efficacy Analysis Set)

Time Point	Statistics	LB 67 mg (N=XX)	Placebo (N=XX)
24 Hours	n	00	00
	Mean	00.00	00.00
	SD	00.000	00.000
	Median	00.00	00.00
	Minimum, Maximum	00.0, 00.0	00.0, 00.0
	Geometric LSM [1]	00.00	00.00
	Geometric LSM Ratio [2]	00.00	
	95% CI for Ratio [2]	00.00, 00.00	
	P-value [2]	0.0000	
Etc.			

CI = confidence interval; LB = liposome bupivacaine, LSM = least squares mean.

If the total amount of opioid used was 0 mg, the value was set to the lesser of 1 mg or one half of the smallest total amount observed in the study prior to being transformed into the natural logarithm.

[1] From an analysis of variance with treatment as the main effect on natural log transformed opioid amount.

Results are presented in the original, non-transformed scale.

[2] Geometric LSM ratio is the anti-log LSM difference (LB/placebo).

Reference: [Listing 16.5.2.1](#).

Pacira Pharmaceuticals, Inc.
402-C-323

Table 14.2.2.11-2 (Page x of Y)
Subjects Who Received Rescue Medication Through 72 Hours
Study Part 2
(Efficacy Analysis Set)

	LB XXX mg (N=XX) n (%)	Placebo (N=XX) n (%)	P-value [1]
Received No Rescue Medication	00 (00.0)	00 (00.0)	
Received Only the First Rescue	00 (00.0)	00 (00.0)	
Received the First Rescue and a Second Opioid Rescue	00 (00.0)	00 (00.0)	
Received all Three Rescues	00 (00.0)	00 (00.0)	

LB = liposome bupivacaine.

[1] P-value is from a chi-square test

Reference: [Listings 16.5.2.1](#) and [16.5.2.2](#).

Pacira Pharmaceuticals, Inc.
402-C-323

Table 14.2.2.12-2 (Page x of Y)
Overall Benefit of Analgesia Score Questionnaire (Total Scores)
Study Part 2
(Efficacy Analysis Set)

Time Point	Statistics	LB XXX mg (N=XX)	Placebo (N=XX)	P-value [1]
24 Hours	n	00	00	0.0000
	Mean	000.0	000.0	
	SD	00.00	00.00	
	Median	0000	0000	
	Minimum, Maximum	000, 000	000, 000	
48 Hours	n	00	00	0.0000
	Mean	000.0	000.0	

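### The 72-hour rescue-category tables place subjects who leave early in the lowest rescue step reached so far, which can overstate the low-rescue rows

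*SAP*

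**What the plan says.** SAP 7.6.2.3 defines four rescue categories from the rescue eCRFs. The no-rescue category "is defined as subjects who report not taking any medication on the four Rescue Medication eCRFs". The first-rescue-only and first-plus-second categories are built the same way: entries on the earlier forms and none on the later ones. None of the definitions mentions length of follow-up.

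The output is Table 14.2.2.11-1 (Part 1) and Table 14.2.2.11-2 (Part 2), titled "Subjects Who Received Rescue Medication Through 72 Hours". Both show n (%) under the column N. The general rule in SAP 7.1, which allows stated exceptions, is that "the denominator for the percentage calculation will be based upon the total number of subjects in the study population for the treatment groups". No exception is stated for these tables. SAP 6 adds: "The efficacy analysis set will include all subjects in the safety analysis set who undergo the planned surgery". So 72 hours of observation is not needed to be in N.

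Protocol 11.6.1 has medications recorded "up to 72 hours after the end of surgery or until the subject is withdrawn from the study, whichever is sooner". Protocol 11.6.3 repeats this limit.

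In Part 2 each category is compared between arms by chi-square (SAP 7.6.2.3). Part 1 is descriptive.

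For time to first opioid rescue, SAP 7.6.2.2 says that a subject given no opioid "will be censored at 72 hours after surgery or at the time of last follow-up, whichever is earliest".

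**The concern.** For a subject who leaves at, say, 10 hours with nothing on the rescue forms, 10 of 72 hours (14%) have been observed. The table still reports that subject as having gone 72 hours without rescue. A subject who leaves after the bolus is likewise reported as having needed only the bolus for 72 hours. The ban on other analgesics also ends at withdrawal (Protocol 11.1), so later analgesic use may occur and would not be recorded.

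Elsewhere the SAP allows for incomplete observation. It censors in the time-to-rescue analysis, projects opioid totals for early discontinuation (7.1.3), and uses subjects with a score as the denominator in the pain-free and satisfaction tables. The rescue-category tables do none of these. The 7.1.3 projection covers amounts only, and a zero amount projects to zero.

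At stake is the accuracy of a percentage that is easily quoted, the share of subjects who needed no rescue. In Part 2 the chi-square tests on these rows are also affected if early leaving differs between arms.

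**Working it through.** **The plan's own figure.** The SAP states no figure for the rescue categories. Its only computable figure is the Part 2 power for the primary endpoint: difference 61, SD 104, 90 per group, two-sided 0.05 (SAP 8). The standard error is 104 × √(2/90) = 15.50 and 61/15.50 = 3.93. Power is Φ(3.93 − 1.96) = 97.6%, or 97.5% with the exact noncentral t. This agrees with the stated >97% but has no bearing on the rescue tables.

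**Direction.** Unobserved time can only hide rescue steps, so a leaver can be placed too low, never too high. The no-rescue row can therefore only be overstated. The two middle rows can gain subjects who would have moved up and lose subjects stuck in the row below, so their net error can go either way.

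**Bound per subject.** One leaver adds 1/90 = 1.1 points to a Part 2 row, or 1/25 = 4 points to a Part 1 row. That is the most by which the row can be overstated per leaver. The error is zero if the leaver would have needed nothing more.

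**Range under assumed rates.** The documents give neither a withdrawal rate nor a rescue rate, so all inputs here are assumptions. Take constant, independent hazards for rescue (r) and for leaving (d).

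- True share free of rescue at 72 h: S = exp(−72r)
- Underlying probability of leaving by 72 h: D = 1 − exp(−72d)
- Share reported under the SAP rule: exp(−72(r+d)) + [d/(r+d)] × [1 − exp(−72(r+d))]

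The first term is subjects with neither event by 72 h. The second is subjects who leave before any rescue.

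Worked case, S = 10% and D = 5%: 72r = 2.3026, 72d = 0.0513, sum 2.3539. The first term is 0.0950. The second is (0.0513/2.3539) × 0.9050 = 0.0197. The reported share is 11.5% against a true 10%.

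| True share | D = 2% | D = 5% | D = 10% | D = 15% |
|---|---|---|---|---|
| 1% | 1.4% | 2.0% | 3.1% | 4.2% |
| 10% | 10.6% | 11.5% | 13.0% | 14.5% |
| 20% | 20.6% | 21.5% | 23.0% | 24.6% |

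The overstatement is about 0.4 to 1.5 points at 2% to 5% leaving and about 2 to 4.6 points at 10% to 15%.

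**Arm comparison.** With 90 per arm, no true difference and a normal approximation to the chi-square test:

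- Leaving 5% in both arms: the reported shares are equal and type I error is 5.0%.
- Leaving 10% against 2%: at S = 10% the reported shares are 13.0% and 10.6%, and type I error is about 7.9%. At S = 20% they are 23.0% and 20.6%, and it is about 6.8%.

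**The case against.** Several points on the other side are sound.

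- **The main withdrawal route cannot inflate the no-rescue row.** Subjects withdrawn for inadequate pain control leave after the rescue regimen has been tried (Protocol 9.1 and 11.1), so their rescue is already recorded. Subjects also stay on site for at least 72 hours. The headline row is affected only by someone who leaves early having had no rescue at all, which may be rare.
- **Consequences are limited.** These are tertiary variables outside the hierarchy. SAP 7.1 switches to exact tests when expected cells fall below 5, and a handful of subjects then rarely decides anything: Fisher's exact p for 5 against 1 of 90 is 0.21.
- **Part of it is already visible.** Disposition tables give early terminations by arm and reason, and Listings 16.1.3 and 16.5.2.1 let individual leavers be traced.

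These points bound the size. They do not change the classification rule, and no planned table shows how many leavers sit in each rescue row.

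A reader might infer that the rescue tables and the time-to-rescue analysis contradict each other. They do not, strictly: one counts any recorded rescue, the other times opioid rescue only, and the time-to-event table itself reports a crude n (%) given an opioid beside the number censored.

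A reader might also take the SAP's censoring as the correct model. It has the same weakness in part. Last follow-up is the later of the last pain score, last medication start and last AE start (SAP 7.6.2.2), and AEs are recorded to Day 30 after withdrawal (Protocol 10.3). A subject who leaves at 10 hours and has an AE starting after 72 hours is censored at 72 hours.

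**Conclusion.** The concern stands as a low-impact flaw in a tertiary table. Taken together, the eCRF-based definition, the full-set denominator, the 72-hour title and the end of recording at withdrawal place early leavers in the lowest rescue category reached. No single SAP sentence says this outright, but no SAP rule points the other way.

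The overstatement is at most 1.1 points per leaver at 90 per arm and 4 points at 25 per arm, and arises only for leavers who would have needed further rescue before 72 hours. Equal leaving in the two arms mainly shifts levels; unequal leaving without rescue distorts the comparison. The 6.8% to 7.9% error rates above depend on an assumed 10% against 2% imbalance that nothing in the documents suggests.

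A large relative bias is also tempting: if one subject in 90 were truly rescue-free, one added leaver would double the figure from 1.1% to 2.2%. That rests on an assumed count, and on the leaver having gone on to need rescue, so the documents do not support it as an estimate.

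**What to change.** In SAP 7.6.2.3 and Tables 14.2.2.11-1 and 14.2.2.11-2:

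1. Add a row, by arm, for subjects not observed to 72 hours who had not reached the third rescue, with the category reached when they left. Take them out of the other rows, so that those rows are true 72-hour outcomes. State which denominator the Part 2 chi-square tests then use.
2. Footnote the Kaplan-Meier estimate of the proportion free of opioid rescue at 72 hours, with its 95% CI, censoring withdrawn subjects at withdrawal and not at a later AE start. The SAP lists only the median and quartiles, but this estimate comes from the same analysis. Note that it covers opioid rescue only.
3. Optionally, count leavers as not meeting the category as a sensitivity analysis. It is less suitable as the main rule, because it turns a leaver who would have needed nothing into a failure.

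The cost is one table row, a changed definition and a footnote, with no new data collection. The reported rescue-free percentage may be slightly lower. The rule should be fixed before unblinding.

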13.1.5. Sensory Function Assessment (Cold Test)

For the sensory function assessment, the subject's sensitivity to cold in the innervated dermatomes (L2, L3) (see [Appendix 7](#)) will be assessed at baseline, when the subject wakes up after surgery (general surgery subjects only), and at 2, 4, 12, 24, 36, 48, 60, and 72 hours after surgery, or until the subject's sensitivity to cold has returned in two consecutive evaluations.

The subject's skin will be wiped with ice or an alcohol pad. The subject will then be asked, "Does this feel cold - yes or no?"

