If a subject's pain is inadequately controlled by opioids, a third rescue, a femoral nerve block, consisting of conventional bupivacaine HCl at a concentration of 0.125% (1.25 mg/mL) at a rate of 8 mL per hour for up to 12 hours may be administered via the previously placed femoral nerve catheter.

Postsurgical Assessments

Postsurgical assessments will include pain intensity scores using the 0-10 point numeric rating scale (NRS) at rest (NRS-R) and NRS with activity (NRS-A) (where the prescribed activity is active knee flexion up to 45 degrees); use of supplemental opioid pain medication; neurological assessment; cardiac assessment (i.e., ECG recordings); sensory function assessment (i.e., cold test); motor function assessment (i.e., 20-meter walk test); vital signs; overall benefit of analgesia score (OBAS) questionnaire; subject satisfaction with postsurgical pain control; physician satisfaction with return of sensory/motor function; and an opioid-related adverse events (ORAEs) questionnaire in Part 1 only. Adverse events (AEs) will be recorded through Day 30. If a cardiac or neurological event occurs during Part 1 or Part 2 of the study that the Investigator believes may be associated with high levels of systemic bupivacaine, an unscheduled PK blood sample should be collected at the time that the event is noted.

Safety and efficacy assessments will be conducted at pre-specified time points after the end of surgery. A follow-up visit will be scheduled for all subjects on Day 30.

See Table 1 in the protocol for the times of each of the assessments.

Pharmacokinetic Assessments (Part 1 only)

Blood samples for PK analysis will be obtained from subjects at specific sites during Part 1 of the study at baseline, 15 minutes, 30 minutes, and 1, 2, 4, 8, 12, 24, 36, 48, 60, and 72 hours after the beginning of study drug administration.

At two sites, there was an addendum to the protocol that allowed for additional blood draws for PK analysis from up to 20 subjects at 84, 96, 120, 144, 168 hours after study drug administration, and on Day 10.

Unscheduled blood samples also may be collected during Part 1 or Part 2 of the study if a cardiac or neurological event occurs that the Investigator believes may be associated with high levels of systemic bupivacaine.

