7.1.2. Imputation of NRS Pain Intensity Scores

For calculation of AUC of NRS pain intensity scores, the windowed worst observation carried forward (wWOCF) and last observation carried forward (LOCF) imputation procedure will be used as follows:

- a) Windowed worst observation carried forward for rescue medications

For subjects who take a rescue medication, their NRS scores recorded within the window of controlled type of rescue medication (see the table below for the windows for the planned rescue medications) will be replaced by the ‘worst’ observation. The worst observation will be the highest score in the time interval from Time 0 to up to the time prior to taking the first rescue medication. The NRS score at the first rescue will be included in this calculation. Note that NRS scores in the window that are higher than the worst value prior to rescue medication will not be overwritten. If no NRS score is available prior to the first rescue the worst observation from all available NRS scores will be used instead.

Medication	Route	Window Used to Impute NRS
Oxycodone	PO	6 hours
Oxycontin (MS Contin)	PO	6 hours
Morphine	IV	4 hours
Hydromorphone (Dilaudid)	IV	2 hours
Hydromorphone (Dilaudid)	PO	4 hours
Fentanyl	IV	6 hours
Fentanyl	Transdermal	Start of administration until the end of the administration plus 6 hours
Hydrocodone	PO	6 hours
Bupivacaine HCl	Perineural	12 hours
Bupivacaine HCl	Infusion	Start of the infusion until the end of the infusion plus 12 hours

Ropivacaine		Start of the infusion until the end of the infusion plus 12 hours
Meperidine	IV	4 hours
Ultram	PO	6 hours

IV = intravenous; PO = oral.

If unplanned rescue medications are given then the window will be determined post-hoc prior to breaking the blind. If a combination opioid is given then the window will be determined by the opioid part of the medication. Opioids given postsurgically with an indication like ‘anesthesia maintenance’ will not be included for imputation purposes.

- b) Missing scores before the first non-missing score will be replaced by the median score at the missing time point from the other subjects in the same treatment group.
- c) Missing scores after the last non-missing score will be replaced by the LOCF.
- d) Missing scores between two non-missing scores will not be replaced (i.e., linear interpolation will be used).

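### Time to sensitivity to cold counts tests taken under the rescue femoral infusion, so a 'no' caused by rescue can delay the recorded return of sensation

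*SAP*

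**What the plan says.** SAP 7.6.2.3 (Time to Sensitivity to Cold) has the event time "defined as the time of the first of two consecutive evaluations when the subject reports sensitivity to cold". Subjects without such a pair are "censored at 72 hours after the end of surgery or at the time of the last follow-up, whichever is earliest". On stopping, it says: "Once a subject reports sensitivity to cold on two consecutive evaluations the subject will no longer be tested". A subject with a single 'yes' therefore goes on being tested. Rescue is not mentioned. Part 2 compares the arms by log-rank test; Part 1 is descriptive.

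Protocol 13.1.5 sets the tests, in dermatomes L2 and L3, on waking (general anesthesia) "and at 2, 4, 12, 24, 36, 48, 60, and 72 hours after surgery", with no instruction about tests during or after a rescue infusion.

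The third rescue is described in SAP 4 as a femoral nerve block with conventional bupivacaine HCl, "at a rate of 8 mL per hour for up to 12 hours may be administered via the previously placed femoral nerve catheter".

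Elsewhere the SAP does allow for this rescue. For the pain AUC, SAP 7.1.2 replaces scores over the window "Start of the infusion until the end of the infusion plus 12 hours", with the same window for ropivacaine. SAP 6 excludes subjects given postsurgical conventional bupivacaine from the PK set. The one planned sensitivity analysis (SAP 7.6.2.1) concerns PCA interval data for the primary variable.

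**The concern.** The rescue acts on the nerve whose recovery the cold test measures. Two effects follow from the rule as written.

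1. A subject with one 'yes' before rescue and a 'no' under the infusion loses the run. The derived time jumps to the first later pair.
2. A subject still numb when rescue starts has any rescue numbness added to the time recorded for the randomized arm.

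Both lengthen the recorded time in whichever arm needs more third rescue. If that is placebo, a real difference narrows or a false one appears in the opposite direction. If it is liposome bupivacaine, the block looks longer than it was. The medians, quartiles and the Part 2 log-rank p-value are exposed.

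The exposure comes from the SAP's change of variable. The protocol's endpoint (12.2) was the proportion sensitive at each time point, where a 'yes' at 4 h counts at 4 h. SAP 7.6.1 replaced it with a time to event.

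**Working it through.** **The plan's own figure.** The documents give no power, effect size or rescue rate for this endpoint. Their one power statement (SAP 8, above 97%) is for the primary AUC. With 61, SD 104 and 90 per arm: 61 / (104 × √(2/90)) = 61 / 15.50 = 3.93, and Φ(3.93 − 1.96) ≈ 97.6% (97.5% by noncentral t). It reproduces and is not touched by this point.

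**Coverage.** Tests fall at 2, 4, 12, 24, 36, 48, 60 and 72 h, so gaps after 4 h are at most 12 h. A 12 h infusion started between 4 and 60 h always covers at least one test. Infusion plus 12 h covers at least two if started between 4 and 48 h.

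**One subject.** 'No' at 2 h, 'yes' at 4 h, infusion 8–20 h.
- Numb during the infusion only: 'no' at 12 h, 'yes' at 24 and 36 h. Recorded time 24 h, which is 24 − 4 = 20 h late.
- Numb to 20 + 12 = 32 h: 'no' at 12 and 24 h, 'yes' at 36 and 48 h. Recorded time 36 h, which is 36 − 4 = 32 h late.

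**Enumeration.** 12 h infusion starting 1 h after the first 'yes'; the last column sets aside tests from infusion start to end plus 12 h.

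| First 'yes' | Current rule, numb during infusion | Current rule, numb infusion + 12 h | Window tests non-evaluable |
|---|---|---|---|
| 4 h | 24 h | 36 h | 4 h |
| 12 h | 36 h | 48 h | 12 h |
| 24 h | 48 h | 60 h | 24 h |
| 36 h | 60 h | censored 72 h | 36 h |
| 48 h | censored 72 h | censored 72 h | censored 72 h |
| 60 h | censored 72 h | censored 72 h | censored 72 h |

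**Group level (simulation).** Assumptions not in the documents: 90 per arm, exponential return times, third rescue in 10% (liposome bupivacaine) and 40% (placebo), start uniform over 6–36 h, numb for a 12 h infusion plus 6 h, every scheduled test available. Negative z means slower return on liposome bupivacaine.

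| Scenario | No rescue effect | Current rule | Window tests non-evaluable | Censor at last pre-infusion test |
|---|---|---|---|---|
| True medians 24 vs 12 h, mean z | −4.2 | −3.1 | −3.6 | about −3.1 |
| Equal medians 12 h, rejection | 3–6% | about 24% | 12% | 12% |

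In the first row about 4 of 90 and 19 of 90 times shift under the current rule; in about 1.5 and 9 of these a 'yes' preceded rescue.

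Other assumptions give less. With equal 24 h medians, rejection is 8.2% under the current rule against 4.0% without rescue effect. With medians 24 vs 2 h and rescue in 5% vs 15%, z moves only from −10.9 to −10.3.

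If rescue instead starts 0–12 h after return of sensation (not before 6 h), with medians 24 vs 12 h, censoring at the last pre-infusion test gives z −1.8, worse than about −2.2 under the current rule.

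**A detail for the fix.** Testing stops after two consecutive 'yes' answers, wherever they fall. Take 'yes' at 4 h, a 2 h infusion from 5 to 7 h (window to 19 h) and 'yes' at 12 h. Testing stops. If the 12 h test is simply discarded, the 4 h 'yes' can never be confirmed and the subject is censored, although the current rule gives 4 h. Enforcing this stop in the first scenario removes the gain in z; keeping window 'yes' answers restores it.

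**The case against.** The strongest objection concerns the estimand. Protocol 9.2 and 12.7 describe the sensory test as a check on restoration of nerve function, not as a measure of how long the study block lasts. Time to confirmed return by randomized arm, whatever rescue was given, is a coherent quantity. That stands, but the SAP does not say it intends this, and it discounts the same rescue for the pain AUC. The cold endpoint is not alone in lacking a rule: the pain-free proportions state none either.

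A reader might infer that an observed return is erased. The documents do not support that. A single 'yes' is unconfirmed by design, every response remains in Listing 16.5.5 and the cold-sensitivity plot, and infusion times are listed. Only the derived time is affected.

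A reader might also infer that the drug's block is overstated, or put a figure on it, such as 5 to 15 percentage points still insensitive at 12–24 h. That range only restates an assumed 5–15% of subjects affected. The documents give no rescue rates, and the net direction cannot be fixed from them. Nor do they say that 0.125% bupivacaine abolishes cold sensation, or for how long; Protocol 7.2 puts bupivacaine's local action at usually under 8 h. Third rescue follows inadequate opioid control, and many saline subjects may be confirmed at 2 and 4 h and leave testing before any infusion.

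**Conclusion.** The point holds as a gap in the derivation of one tertiary endpoint. The rule counts tests taken under a rescue block of the nerve being tested, and this can bias the medians and the Part 2 log-rank test. For an affected subject the shift in the worked example is 20 to 32 h, if the rescue abolishes cold sensation for the periods assumed. Across arms it ranges from negligible to a false-rejection rate near 24%, depending on assumed rescue rates, return times and duration of numbness. Direction is unknown.

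The primary and secondary analyses and the stated power are unaffected. Subjects with two consecutive 'yes' answers before rescue are protected. The change is worth making because it is cheap and uses data already collected.

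**What to change.** In SAP 7.6.2.3, treat cold tests from the start of any local anesthetic rescue infusion to its end plus 12 h (the 7.1.2 window) as non-evaluable. Apply the two-consecutive rule to the remaining evaluable tests, so that a 'yes' before rescue confirmed by the next evaluable 'yes' keeps its observed time. Add one sentence for the stop rule: a 'yes' inside the window stays usable, since the rescue block cannot produce it, so subjects whose testing ended on such an answer are not censored by the derivation.

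Report the number of affected subjects per arm in Tables 14.2.2.14-1 and 14.2.2.14-2, and keep the current rule as a supportive analysis. Do not censor at the last pre-infusion test: in the worked example that discards the 4 h 'yes', and the censoring is likely to be informative.

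The cost is one SAP paragraph and one derivation, using infusion times in Listings 16.5.2.2 and 16.5.2.3. Conduct does not change. Three limits remain: the 12 h tail is borrowed from the pain-score rule, some late returns stay censored at 72 h, and subjects still numb when rescue starts are only partly corrected.
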